6.4.1 Temporary discontinuation of IMP

6.4.1.1 Serious infection

Treatment must be discontinued if study participant has a serious infective episode requiring eg, hospitalization, or iv antibiotic therapy (including but not limited to bacteremia or sepsis, bacterial meningitis, osteomyelitis or septic arthritis, bacterial pneumonia, or visceral abscess).

6.4.1.2 Hypogammaglobulinemia and non-serious persisting or recurrent infection

In the event of a non-serious infection, the Benefit-Risk of continuing treatment with IMP must be carefully evaluated by the Investigator in collaboration with the Medical Monitor and the Study Physician. Treatment may be temporarily discontinued for the study participant who develops a non-serious persisting or recurrent infection with a serum total IgG levels between $\geq 1\text{g/L}$ and $<2\text{g/L}$ (see Section 7.9). Upon resolution of infection and the IgG levels returning to $\geq 2\text{g/L}$, the study participant may be allowed to restart treatment with IMP (at the same dose for study participants in Treatment Period Part 1, or at the same dose or at the reduced dose of [REDACTED] for study participants in Treatment Period Part 2) at the discretion of the investigator and in agreement with Medical Monitor and Study Physician, if the study participant is willing and if the benefit-risk remains favorable for the study participant.

6.4.1.3 Hypogammaglobulinemia irrespective of infection

Treatment will be temporarily discontinued for the study participant who develops an event of hypogammaglobulinemia with a serum total IgG $<1\text{g/L}$ (see Section 7.9) irrespective of infection. When the IgG level reaches $\geq 2\text{g/L}$, the study participant may be allowed to restart treatment with IMP (at the same dose for study participants in Treatment Period Part 1, or at the same dose or at the reduced dose of [REDACTED] for study participants in Treatment Period Part 2) at the discretion of the investigator and in agreement with Medical Monitor and Study Physician, if the study participant is willing and if the benefit-risk remains favorable for the study participant.

6.4.2 Potential drug-induced liver injury IMP discontinuation criteria

Study participants with potential drug-induced liver injury (PDILI) must be assessed to determine if IMP must be discontinued. In addition, all concomitant medications and herbal supplements that are not medically necessary should also be discontinued.

The PDILI criteria below require **immediate and permanent** discontinuation of IMP:

- Study participants with either of the following:
 - ALT or AST $\geq 5\text{xULN}$
 - ALT or AST $\geq 3\text{xULN}$ and coexisting total bilirubin $\geq 2\text{xULN}$

The PDILI criterion below requires immediate discontinuation of IMP:

- Study participants with ALT or AST $\geq 3\text{xULN}$ who exhibit temporally associated symptoms of hepatitis or hypersensitivity. Hepatitis symptoms include fatigue, nausea, vomiting, right upper quadrant pain or tenderness. Hypersensitivity symptoms include fever (without clear alternative cause), rash, or eosinophilia (ie, $>5\%$).

If a nondrug-related cause for the symptoms can be confirmed, these study participants may resume IMP administration after discussion with the responsible UCB physician, but only when the requirements for rechallenge with IMP as provided in Section 9.2.1.2.1 are followed.

The PDILI criterion below allows for study participants to continue on IMP at the discretion of the investigator.

- Study participants with ALT or AST $\geq 3 \times$ ULN (and $\geq 2 \times$ Baseline) and $< 5 \times$ ULN, total bilirubin $< 2 \times$ ULN, and no eosinophilia (ie, $\leq 5\%$), with no fever, rash, or symptoms of hepatitis (eg, fatigue, nausea, vomiting, right upper quadrant pain or tenderness).

Evaluation of PDILI must be initiated as described in Section 9.2.1. If study participants are unable to comply with the applicable monitoring schedule, IMP must be discontinued immediately.

Investigators should attempt to obtain information on study participants in the case of IMP discontinuation to complete the final evaluation. Study participants with PDILI should not be withdrawn from the study until investigation and monitoring are complete. All results of these evaluations and observations, as well as the reason(s) for IMP discontinuation and study participant withdrawal (if applicable), must be recorded in the source documents. The eCRF must document the primary reason for IMP discontinuation.

7 STUDY TREATMENT

7.1 Description of investigational medicinal product

[REDACTED]

Details of the IMP and its specifications are provided in the IMP Handling Manual.

7.2 Treatment to be administered

The initial dose administered will be based on the dose at the time of completion of the Treatment Period from the parent study (eg, CIDP01). For subjects who had a gap period between the parent study (eg, CIDP01) and CIDP04, a starting dose of [REDACTED] will be used (see Table 7-1). The dose used in the study may be reduced based on individual tolerability to [REDACTED] (see Table 7-2) (eg, severe headache) but the maximum dose used will be [REDACTED]. The dose used during Treatment Period Part 2 may be reduced to [REDACTED] in case of recurrent low observed IgG levels for a participant. Treatment temporary halt may also be implemented in some situation (see Section 6.4.1).

Eligible study participants will receive rozanolixizumab [REDACTED] by sc infusion for 24 weeks during Treatment Period Part 1 (from Visit 2 to Visit 25) and during an optional additional 52 weeks during Treatment Period Part 2. Treatment Period 2 may be shortened depending on availability of an Access Program or equivalent.

Study participants may choose to self-administer the IMP during Treatment Period Part 2 under supervision of a nurse and after having received appropriate training.

Table 7-1: IMP doses to be administered (equivalent to approximately [REDACTED]) by body weight

Body weight ranges	IMP doses to be administered (equivalent to approximately [REDACTED] ^a)	IMP volume to be administered
≥40 to <49kg	[REDACTED]	[REDACTED]
≥49 to <63kg	[REDACTED]	[REDACTED]
≥63 to <77kg	[REDACTED]	[REDACTED]
≥77 to <91kg	[REDACTED]	[REDACTED]
≥91 to <105kg	[REDACTED]	[REDACTED]
≥105 to <119kg	[REDACTED]	[REDACTED]
≥119 to <133kg	[REDACTED]	[REDACTED]
≥133 to <147kg	[REDACTED]	[REDACTED]
≥147 to <161kg	[REDACTED]	[REDACTED]
≥161 to 170kg	[REDACTED]	[REDACTED]

IMP= investigational medicinal product

^a Doses administered will be ±10% of the intended dose, except for study participants with a body weight of 47 to 50kg and 63kg.**Table 7-2: IMP doses to be administered (equivalent to approximately [REDACTED]) by body weight**

Body weight ranges	IMP doses to be administered (equivalent to approximately [REDACTED])	IMP volume to be administered
≥40 to <49kg	[REDACTED]	[REDACTED]
≥49 to <69kg	[REDACTED]	[REDACTED]
≥69 to <89kg	[REDACTED]	[REDACTED]
≥89 to <109kg	[REDACTED]	[REDACTED]
≥109 to <129kg	[REDACTED]	[REDACTED]
≥129 to <149kg	[REDACTED]	[REDACTED]
≥149 to <169kg	[REDACTED]	[REDACTED]
≥169 to 170kg	[REDACTED]	[REDACTED]

IMP= investigational medicinal product

The IMP will be administered at the clinic or in a home setting (refer to [Table 5-1](#) for details). Home administration is study participant to a set of conditions (see [Section 8.2](#)) to ensure study participant safety.

The IMP will be administered as a sc infusion using a syringe pump. [REDACTED]

[REDACTED]
[REDACTED]
[REDACTED]
[REDACTED]
[REDACTED] The chronology of these events should be recorded accurately in the source data and eCRF.

The study participant's body weight at entry into CIDP04 (either at Screening [Visit 1] or Baseline [Visit 2]) will be used to select the volume for dose infusion throughout Treatment Period Part 1. Body weight will be reevaluated at start of the Treatment Period Part 2, and every 6 months, and will be used to select the correct volume for dose infusion from these timepoints.

The exact procedure for dose preparation according to body weight will be provided in the IMP Handling Manual.

7.3 Packaging

[REDACTED]
[REDACTED]

Details of the IMP and its specifications are provided in the IMP Handling Manual.

7.4 Labeling

Clinical drug supplies will be labeled in accordance with the current ICH guidelines on Good Clinical Practice (GCP) and Good Manufacturing Practice and will include any locally required statements. If necessary, labels will be translated into the local language.

7.5 Handling and storage requirements

The investigator (or designee) is responsible for the safe and proper storage of IMP at the site. Investigational medicinal product stored by the investigator is to be kept in a secured area with limited access according to the storage conditions mentioned on the label.

Appropriate storage conditions must be ensured either by controlling the temperature (eg, room, refrigeration unit) or by completion of a temperature log in accordance with local requirements on a regular basis (eg, every work day), showing actual and minimum/maximum temperatures reached over the time interval.

In case an out-of-range temperature is noted, it must be immediately reported as per instructions contained in the IMP Handling Manual.

The investigator (or designee) will instruct the study participant to store the IMP following the instructions on the label.

7.6 Drug accountability

A Drug Accountability form will be used to record IMP dispensing and return information on a by-study participant basis and will serve as source documentation during the course of the study. Details of any IMP lost, damaged (due to breakage or wastage), not used, partially used,

disposed of at the study site, or returned to the sponsor or designee must also be recorded on the appropriate forms. All supplies and pharmacy documentation must be made available throughout the study for UCB (or designee) to review.

The investigator (or designee) is responsible for retaining all used, unused, and partially used containers of IMP until returned or destroyed (all details are provided in the IMP Handling Manual).

The investigator may assign some of the investigator's duties for drug accountability at the study site to an appropriate pharmacist/designee.

The investigator must ensure that the IMP is used only in accordance with the protocol.

Periodically, and/or after completion of the clinical phase of the study, all used (including empty containers)/partially used, unused, damaged, and/or expired IMP must be reconciled and either destroyed at the site according to local laws, regulations, and UCB Standard Operating Procedures (SOPs) or returned to UCB (or designee). Investigational medicinal product intended for the study cannot be used for any other purpose than that described in this protocol.

7.7 Procedures for monitoring study participant compliance

Study participant compliance will be ensured by the administration of IMP by sc infusion by designated site personnel. Drug accountability must be recorded on the Drug Accountability form.

7.8 Concomitant medications/treatments

7.8.1 Permitted concomitant treatments (medications and therapies)

Concomitant treatments/medications permitted at a stable dose during the course of the study are detailed in [Table 7-3](#).

Table 7-3: Permitted concomitant medications

Permitted medication	Allowed dosages	Comment
Oral corticosteroids (prednisolone)	$\leq 30\text{mg/day}$	Stable [REDACTED] prior to entry
Methotrexate	$\leq 30\text{mg/week}$	[REDACTED] stable dose [REDACTED] prior to entry
Mycophenolate mofetil	$\leq 3\text{g/day}$	[REDACTED] stable dose [REDACTED] prior to entry
Cyclosporine ^a	$\leq 5\text{mg/kg/day}$ for unmodified $\leq 4\text{mg/kg/day}$ for modified (microemulsion)	[REDACTED] stable dose [REDACTED] prior to entry
Azathioprine	$\leq 3\text{mg/kg/day}$	[REDACTED] stable dose [REDACTED] prior to entry
Tacrolimus ^b	$\leq 5\text{mg/day}$	[REDACTED] stable dose [REDACTED] prior to entry

^a Doses higher than listed are permissible if plasma trough level is $\leq 300\text{ng/L}$.

^b If the total daily weight-based dose is $>5\text{mg}$, then a plasma trough level should be checked to ensure study participant is not above the recommended therapeutic range.

The use of cannabidiols and medicinal marijuana (prescribed by a physician) is also permitted. When applicable, the study participant must be on a stable dose of cannabidiols and/or medicinal marijuana for [REDACTED] prior to Screening Visit and remain stable for the duration of the study.

7.8.2 Prohibited concomitant treatments (medications and therapies)

The following concomitant medications are prohibited during the Treatment Period:

- IVIg and SC Ig (refer to Section 7.8.3)
- All biologics including rituximab
- Cyclophosphamide
- Pimecrolimus
- IPP-201101 (Lupuzor™)
- Systemic dexamethasone
- PLEX
- IA

If a study participant requires or takes IVIg, SC Ig, PLEX, dexamethasone, or rituximab, they must be discontinued from IMP. In all other cases of intake of prohibited concomitant medication, the investigator will (where possible) discuss with the Medical Monitor and/or Sponsor Study Physician and a decision will be made whether the study participant should discontinue IMP (see Section 6.4).

If a study participant is discontinued from IMP they should be encouraged to complete Visit 26/PEOT and complete the Observation Period (see [Table 5-1](#) and Section [6.4](#)).

7.8.3 Rescue medication

If, at any time during this OLE study, a study participant relapses according to the predefined criteria for relapse as specified in Section [4.2.1](#) using the study participant's score on iRODS, INCAT, or maximum grip strength as assessed by the site personnel and supported by the medical judgement of the investigator, then rescue therapy must be considered and the study participant withdrawn from IMP (see Section [6.4](#)). The study participant will return to the SOC Ig treatment (eg, IVIg of 2g/kg) at the investigator's discretion.

7.9 Blinding

Not applicable; this is an open-label study. However, in order to maintain the blind of the parent study (eg, CIDP01) study participant's IgG levels will be blinded to the investigator for the initial 4 weeks treatment of every study participant in CIDP04. The duration of 4 weeks may be adjusted during the course of the study based on results from CIDP01 and CIDP04.

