5 STUDY DESIGN

5.1 Study description

This is a Phase 2A, multicenter, single-arm, OLE study to evaluate the safety, tolerability, and efficacy of rozanolixizumab during long-term treatment of study participants with CIDP from a previous study with rozanolixizumab.

Access to CIDP04 for study participants coming from CIDP01: Study participants from CIDP01 who have completed the Treatment Period (ie, all visits up to Visit 17) without a relapse of CIDP will be offered the opportunity to be directly enrolled into this OLE study. Study participants will enter CIDP04 on the same day as the last study visit in CIDP01: Visit 17. Study participants from CIDP01 who have experienced a relapse of CIDP (during either the Treatment Period or the Observation Period), have been successfully rescued and stabilized with SOC medication and have consented to enter this OLE study, may be assessed for eligibility. The study participants who relapsed during the Treatment Period of CIDP01 will be offered entry into CIDP04 only once CIDP01 study results are available, after the blind has been broken at the end of the study, and it is confirmed they received placebo in CIDP01.

In case the study participants have a gap period between the end of the parent study and the start of this OLE study (ie, last visit in the parent study does not take place on the same day as entry of study CIDP04), a Screening Period of 2 to 5 weeks will be applicable to confirm that the study participant still meets the eligibility criteria for entry in the OLE study and allow for a smooth transition between the treatment used by the study participants during the gap period and the initiation of rozanolixizumab. The CIDP04 study includes a first 24-week Treatment Period (Part 1) followed by a second Treatment Period (Part 2) of up to 52 weeks (or until an Access Program or equivalent is in place, whichever comes first). Entry to the Treatment Period (Part 2) will be contingent to a favorable individual benefit-risk after careful individual assessment has been performed for each study participant completing Treatment Period (Part 1). An 8-week Observation Period will be followed in case of premature termination or after completion of the Treatment Periods (either at end of Part 1 for study participants not continuing in Part 2 or at end

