7.10 Randomization and numbering of study participants

Randomization is not applicable in the current study. Study participants will be identified with the study participant number they received in the parent study.

An interactive response technology (IRT) will generate individual assignments for study participants, as appropriate, according to the visit schedule and the dose the study participant should receive.

The study participant number will be required in all communication between the investigator or designee and the IRT regarding a particular study participant.

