9.1.7 Safety signal detection

Selected data from this study will be reviewed periodically to detect as early as possible any safety concern(s) related to the IMP so that investigators, clinical study participants, regulatory authorities, and IRBs/IECs will be informed appropriately and as early as possible. A DMC will be responsible for monitoring safety data during the study. Further details are provided in Section 14.7.

The Study Physician or medically qualified designee/equivalent will conduct an ongoing review of SAEs and perform ongoing SAE reconciliations in collaboration with the PS representative.

As appropriate for the stage of development and accumulated experience with the IMP, medically qualified personnel at UCB may identify additional safety measures (eg, AEs, vital signs, laboratory or ECG results) for which data will be periodically reviewed during the course of the study.

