9.2.1.1 Consultation with Medical Monitor and local hepatologist

Potential drug-induced liver injury events require notification of the Medical Monitor within 24h (eg, by laboratory alert), and the study participant must be discussed with the Medical Monitor as soon as possible. If required, the study participant must also be discussed with the local hepatologist. The local hepatologist is the expert usually consulted by the treating physician for assessment and management of potential hepatic disease. This would usually be a hepatologist, but may be a gastroenterologist. If determined necessary, this discussion should be followed by a full hepatology assessment (see Section 9.2.1.3) and SAE report (if applicable).

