14.7 Planned interim analysis and data monitoring

A DMC will systematically monitor and report on the progress, safety, and/or critical efficacy endpoints of this study by convening to review the ongoing program safety and efficacy data. The DMC will also review the impact of infusion rate on local and systemic tolerability during the first 2 doses.

A DMC charter will define the composition, roles, and responsibilities of the DMC, specify the data to be reviewed and determine the procedures to be followed. Ad hoc DMC meetings can be held for reasons determined appropriate by the sponsor.

The deliberations and decisions of the DMC will be formally documented.

A detailed description of the DMC composition, processes, and responsibilities will be provided in a separate DMC charter.

Two interim analyses will be conducted. Firstly at the time of the lock of the parent study CIPD01 and additionally once all study participants have completed Part 1 of the Treatment Period in CIDP04 and have either entered into the Treatment Period Part 2 or the Observation Period. Details of the planned analyses will be fully outlined in the respective SAPs.

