10.3 Clinical laboratory evaluations

Laboratory data (chemistry, hematology and urinalysis) and changes from Baseline (if applicable) for numeric variables will be listed by treatment group and timepoint. Any laboratory measurements that are BLQ or ALQ will be handled as described in [Section 4.2.2](#). Values outside the reference range for the numeric variables will be flagged in the listings. The reference ranges will also be reported in the listings. In addition, the listings will include a flag for values identified as markedly abnormal MA as defined by the criteria outlined in [Section 13.2](#)**Error! Reference source not found..**

Chemistry and hematology parameters will be summarized by treatment group for both absolute values and changes from Baseline.

The laboratory variables to be included in the analysis are presented in [Table 10-1](#).

Table 10-1: Laboratory measurements

Category	Panel	Variable
Hematology	Red blood cell	RBC count, hemoglobin, hematocrit
	White blood cell	WBC count
	White blood cell differential	Absolute counts: ANC, basophils, eosinophils, ALC, monocytes Percentages: neutrophils/leukocytes, basophils/leukocytes, eosinophils/leukocytes, lymphocytes/leukocytes, monocytes/leukocytes

Table 10–1: Laboratory measurements

Category	Panel	Variable
	Platelet	Platelet count
Chemistry	Liver function	ALP, ALT, AST, GGT, total bilirubin ^a , LDH
	Enzymes	Creatine kinase, amylase
	Proteins	Total protein, albumin, alpha- and beta- globulins, hsCRP
	Kidney Function	Urea- nitrogen, creatinine
	Lipids	Triglycerides, total cholesterol, LDL cholesterol, HDL cholesterol,
	Electrolytes	Calcium, phosphate, sodium, potassium, chloride, and magnesium
	Hormones	Procalcitonin
Urinalysis ^b	Dipstick	pH, nitrite, protein, glucose, ketones, urobilinogen, bilirubin, blood,
	Urine Sediment	Leukocytes
	Quantitative	Albumin, creatinine, protein

ALC=absolute lymphocyte count; ALP=alkaline phosphatase; ALT=alanine aminotransferase; ANC=absolute neutrophil count; AST=aspartate aminotransferase; GGT=gamma-glutamyltransferase; HDL=high density lipoprotein; hsCRP=high sensitivity C-Reactive Protein; LDH=lactate dehydrogenase; LDL=low density lipoprotein; RBC=red blood cell; WBC=white blood cell

^a Direct bilirubin will also be measured when total bilirubin is elevated.

^b Urine microscopy will be performed if urine is positive for protein, blood, nitrite, or leukocytes.

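### Protocol 7.9 hides IgG from the investigator for the first four doses, and no one is given the task of starting the mandatory IgG hold in that window

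*Protocol*

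**What the plan says.** **The blind.** Protocol 7.9 (Blinding) explains that, to protect the parent-study blind, "IgG levels will be blinded to the investigator for the initial 4 weeks treatment of every study participant in CIDP04". It allows the length of the window to be changed in the light of CIDP01 and CIDP04 results.

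**The hold.** Protocol 6.4.1.3 reads "Treatment will be temporarily discontinued for the study participant who develops an event of hypogammaglobulinemia with a serum total IgG" below 1 g/L, whether or not there is an infection, and refers the reader to 7.9. Restart needs IgG of at least 2 g/L and is left to the investigator, with the agreement of the Medical Monitor and Study Physician. Protocol 6.4.1.2 (IgG from 1 to below 2 g/L with a persisting or recurrent non-serious infection) also points to 7.9.

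**Other places where a route might be stated.**
- Protocol 7.10: the IRT "will generate individual assignments for study participants, as appropriate, according to the visit schedule and the dose the study participant should receive". IgG is not mentioned.
- Protocol 9.1.7: "Selected data from this study will be reviewed periodically to detect as early as possible any safety concern(s) related to the IMP".
- Protocol 14.7: a DMC charter will "specify the data to be reviewed and determine the procedures to be followed".
- SAP 10.3: "the listings will include a flag for values identified as markedly abnormal". SAP Table 13-2 puts the IgG criterion at 1 g/L or less.

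**A comparison.** For liver events, Protocol 9.2.1.1 names the recipient, the deadline and a mechanism: "Potential drug-induced liver injury events require notification of the Medical Monitor within 24h (eg, by laboratory alert").

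**The concern.** One rule takes away the input that another, mandatory, safety rule needs. Lowering IgG is the drug's intended effect, and 6.4.1.3 sets the level at which dosing must stop. For the first four weekly doses the person giving the drug may not see that level, and the plan does not say who watches it instead. The cross-reference from 6.4.1.3 to 7.9 shows that the authors saw the link, but 7.9 contains no procedure.

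A site that follows 7.9 and the visit lists as written would go on dosing after a result that should have stopped treatment, in a study whose primary objective is safety and tolerability.

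**Working it through.** The plan gives no figure here to reproduce. The check has two parts: a comparison of the sections, and a count of doses.

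**1. Does any section assign the hold in the blinded weeks?**
- 7.9 names the investigator as blinded and names nobody who reads the value instead.
- 6.4.1.3 is written in the passive. The Medical Monitor and Study Physician appear only at restart.
- Footnote w of Table 5-1 asks for weekly IgG monitoring below 2, with no responsible person.
- The lists for Visits 2 to 5 (8.2.1 to 8.2.4) include dosing with no IgG condition. The list for Part 2 home visits (8.3.2) does make dosing conditional on 6.4.1.3.
- Review under 9.1.7 is periodic. The DMC role in 14.7 is general and leaves the detail to its charter. The SAP flag is for reporting and does not control dosing.

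No section assigns it.

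**2. How many doses could follow a low result?**

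Inputs:
- Doses in the window are at Visits 2, 3, 4 and 5 (Weeks 1 to 4), one per week (8.2.1 to 8.2.4).
- Total IgG is scheduled at each of these visits and sampled before the dose. For direct entrants the Visit 2 value is the CIDP01 last-visit value (Table 5-1, footnote f; 8.2.1).
- Turnaround *k* is not stated. I assume 1 or 2 weeks. Protocol 9.2 sends the safety laboratory parameters to a central laboratory, and 11.2 has the IgG samples drawn with them, so a result before the same visit's dose cannot be presumed.

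With a first low sample at Visit *v*, the first dose that the result could stop is at Visit *v + k*. The last dose in the window is at Visit 5. Hence

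doses in the window that could follow the result = max(0, 5 − (*v* + *k*) + 1) = max(0, 6 − *v* − *k*).

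| First low at | *k* = 1 week | *k* = 2 weeks |
|---|---|---|
| Visit 2 | 6 − 2 − 1 = 3 | 6 − 2 − 2 = 2 |
| Visit 3 | 6 − 3 − 1 = 2 | 6 − 3 − 2 = 1 |
| Visit 4 | 6 − 4 − 1 = 1 | 6 − 4 − 2 = 0 |
| Visit 5 | 6 − 5 − 1 = 0 | max(0, −1) = 0 |

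The Visit 2 row is relevant mainly to direct entrants who received active drug in CIDP01, since the eligibility criteria set no lower limit for total IgG. Visit 3 is the first sample affected by study drug for newly treated participants. Gap entrants come in on stable immunoglobulin (inclusion criterion 6).

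**The case against.** The strongest reply is that this is an omission and not a conflict. 6.4.1.3 does not make the investigator the trigger, 7.9 blinds only the investigator, and the Medical Monitor and Study Physician may see IgG throughout. Both rules can be obeyed at once if one of them acts. The laboratory manual, DMC charter and DMC SAP are not among the documents, and any of them may contain an alert. This stands, and it limits the point to a missing stated route. A reader might infer that nobody could stop dosing; the documents do not support that.

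A reader might also infer that as many as four doses follow a low result. That needs the result back before the dose at the same visit. If it is not back that day, the dose is given with or without the blind, so it cannot be charged to 7.9. The count should start at a 1-week turnaround.

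The counts are conditional. Nothing shows that IgG falls below 1 g/L after one dose, and whether a low value at the end of CIDP01 was already being managed depends on rules not available here. There are also safeguards: the first four weeks are all on site, a serious infection stops treatment whatever the IgG (6.4.1.1), and the DMC meets for CIDP04 together with CIDP01 (SAP 4.4.1). These reduce the concern, but none of them starts the IgG hold.

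Finally, a hold in these weeks may hint at active treatment in CIDP01, most of all at Visit 2. That is true, but 6.4.1.3 already requires the hold.

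**Conclusion.** The point holds in this form: for the doses at Visits 2 to 5, the protocol's mandatory hold at IgG below 1 g/L has no stated route by which it would be started. With an assumed turnaround of 1 to 2 weeks, between 0 and 3 doses in the window could follow a first low result, depending on the visit. How often IgG falls below 1 g/L is not given, so the size of the risk is unknown. The finding would fall away if the laboratory manual or DMC charter already routes such results to an unblinded person. It should be corrected, because the gap concerns a mandatory safety rule and costs little to close.

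A secondary point is that the blind covers every participant. Those who relapsed in the CIDP01 Treatment Period enter only "after the blind has been broken at the end of the study, and it is confirmed they received placebo in CIDP01", when the stated reason for the blind no longer applies. One might infer that the plan fixes the blind for this group regardless. It does not, because 7.9 lets the duration be adjusted on CIDP01 results; it only fails to say that it will be.

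**What to change.** In Protocol 7.9, state that the central laboratory alerts the Medical Monitor, who is not blinded under 7.9, to any total IgG below 1 g/L during the blinded window. State also that this person places and releases the 6.4.1.3 hold without disclosing the value, for example through the IRT. If such an alert already exists in another study document, a reference to it in 7.9 is enough.

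In the same section, replace the permission to adjust the window with a statement that the IgG blind ends, and does not apply to new entrants, once the parent study is unblinded.

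The cost of the first change is two sentences, a laboratory alert and a means of placing the hold. The second costs nothing beyond its wording. The downside is that a hold may suggest active parent-study treatment while CIDP01 is still blinded.
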